## **Reporting**

All device or procedure-related adverse events will be captured from enrollment through the completion of the study on the Adverse Event Case Report Form (CRF). However, in accordance with ISO 14155 latest version when using commercial medical devices, device deficiencies, SAEs, SADEs and USADEs must be reported per the post-market surveillance/vigilance system of the manufacturer as specified in the manufacturer's labeling/manuals.

All AEs, Device Deficiencies, SAEs, SADEs and USADEs (see list in section C) reported during the study will document severity, treatment/intervention provided, relationship to the device/procedure, and resolution. Any USADEs and/or deaths occurring during the study procedures will also be evaluated to determine whether the SCS system might have malfunctioned, or caused or contributed to the event.

All SAEs/SADEs/USADEs will be documented and reported to SGX as soon as possible, but no later than 24 hours after becoming aware of the SAE.

The SGX contact information for these events is or reporting through eCRF:

E-mail: [[contact]](mailto:[contact])

The Investigator or site staff may report an event to the sponsor by email, telephone or fax initially, but must follow-up by completing an Adverse Event CRF. The monitored CRF should be sent to SGX and, if possible, be accompanied by copies of source documentation regarding the event (e.g., physician / nurse notes or summaries / hospitalizations records). The Investigator must also report the SAE to the EC according to their local regulations.

An attempt must be made by the Investigator/site staff to schedule a subject visit as soon as feasible following the report of the SAE. In the event of a subject death, all available information (e.g. autopsy or other post-mortem findings) should be provided on the CRF. An Investigator shall submit a report to the sponsor of any USADE occurring during the study as soon as possible, but in no event later than 10 working days after the Investigator first learns of the effect. SGX will conduct an evaluation of the event to determine whether the event is an anticipated event based on labeling and risk analysis. The Investigator must also report the event to the EC if it is determined to be unanticipated.

All AEs will be followed until the event is resolved (with or without sequelae). If a device-related event is ongoing at the time of study completion or termination, the subject will be followed until resolution or the Investigator determines that the subject's condition is stable.

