## **B.2. Study Objectives**

The **primary objective** of this study is to evaluate the clinical effectiveness of DTM™ SCS with CMM in reducing back pain as compared to CMM alone for the treatment of intractable chronic back pain.

The **secondary objectives** of this study are to further document the safety, clinical effectiveness and health economic analytics of the DTM™ SCS delivered through Intellis™ system when compared to CMM alone, for the treatment of chronic pain of the trunk and limbs.

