#### Definitions

An **Adverse Event** (AE) is any untoward medical occurrence defined as an unintended disease or injury or untoward clinical signs (including abnormal laboratory findings deemed clinically significant as determined by the investigator) in a subject whether or not related to the investigational or commercial medical device. This definition includes events related to the study medical devices and events related to the study procedures. An AE is also any event related to any underlying medical condition, present at Baseline, which increases in severity by a clinically meaningful amount during the study as determined by the Investigator.

For all adverse events, the Investigator will provide an assessment of the adverse event, its severity, treatment/intervention provided, relationship to the device/procedure, and resolution.

As the primary efficacy measure in this study is pain, back or leg pain does *not* need to be reported as an adverse event unless it meets the definition of a serious adverse event. However, Investigators may, at their discretion, report any pain-related adverse events during the study.

Pre-existing conditions will not be reported as an adverse event unless there has been a substantial increase in the severity or frequency of the problem which has not been

attributed to natural history.

**A Serious Adverse Event (SAE)** is an adverse event that

- Led to death
- Led to serious deterioration in the health of the subject, that either resulted in
  - a life-threatening illness or injury (life-threatening is defined as at risk of death at the time of the event), or
  - a permanent impairment of a body structure or a body function, or
  - in-patient hospitalization or prolongation of existing hospitalization (in-patient hospitalization is defined as a hospital admission for a period of greater than 24 hours), or
  - medical or surgical intervention to prevent life-threatening illness or injury or permanent impairment to a body structure or a body function,
- Led to fetal distress, fetal death, or a congenital abnormality or birth defect

Those known adverse events related to the device, procedure or therapy are listed in the Risk Analysis Section C.

**A Serious Adverse Device Effect (SADE)** is an adverse device effect that has resulted in any of the consequences characteristic of a serious adverse event.

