### **B.8.2. Safety Measurements**

**Adverse Events:** Subjects will be assessed for adverse events starting at enrollment and continuing through to study completion. If an adverse event occurs, an adverse event CRF will be completed. The event will be followed until resolution or determination that the subject's condition is stable.

The Investigators shall categorize all adverse events for seriousness, severity, and relationship. All determinations of severity, device relation, and resolution are made by the Investigator and not by the Sponsor.

For purposes of consistent adverse event reporting and analysis, adverse events will be categorized using the Medical Dictionary for Regulatory Activities (MedDRA®) terminology, consistent with the *MedDRA® Term Selection: Points to Consider* document. Events are grouped by System Organ Classification (SOC) and Preferred Term (PT), according to diagnosis and/or event description as provided by the Investigator on the case report form.

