5.9 Safety Analyses

Safety will be assessed by characterizing adverse events at all study visits with descriptive statistics.

All Adverse Events assessed/determined to be study-related study will document seriousness, severity, treatment/intervention provided, relationship to the device/procedure, and resolution.

Adverse events (AE) will be reported for the mITT set. A sensitivity analysis of AEs based on the ITT set will also be performed. AEs will be tabulated with the number of events and subjects with event for each event type and overall. Rates will be reported as the number of subjects who experience at least one event during the analysis interval out of the total number of subjects with follow-up to the beginning of the analysis interval. Serious adverse events will also be tabulated. The rate of all AEs and SAEs reported in the study will be reported.

All AEs and SAEs will also be summarized by relatedness as described above. Adverse events leading to death or study discontinuation will be provided in listing format.

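### The adverse event capture rule is inconsistent across the protocol and SAP, so non-serious events under CMM may be under-recorded, unevenly between arms and sites

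*Protocol*

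**What the plan says.** Three places describe which adverse events are recorded, each with a different scope.

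- **Protocol B.7.6, Reporting:** "All device or procedure-related adverse events will be captured from enrollment through the completion of the study" on the adverse event form. The sentence names related events and is silent on others.
- **Protocol B.8.2, Safety Measurements:** "Subjects will be assessed for adverse events starting at enrollment and continuing through to study completion", and "If an adverse event occurs, an adverse event CRF will be completed". There is no condition on relatedness.
- **SAP 5.9:** "All Adverse Events assessed/determined to be study-related study will document seriousness", along with severity, treatment, relationship and resolution. The same section then promises the rate of all reported AEs and SAEs, and a summary by relatedness.

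Other text bears on the reading. B.7.6, Definitions, counts an untoward occurrence "in a subject whether or not related to the investigational or commercial medical device", and adds: "For all adverse events, the Investigator will provide an assessment of the adverse event, its severity". The Reporting part also says: "All SAEs/SADEs/USADEs will be documented and reported to SGX as soon as possible", with no relatedness condition. Section B.6.16 has control subjects assessed for adverse events at each scheduled visit. Under B.2, a secondary objective is to "further document the safety, clinical effectiveness and health economic analytics" of DTM SCS against CMM alone.

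**The concern.** The B.7.6 qualifier refers to a device that only one arm has. Control subjects receive drugs, injections, ablation and other interventions listed in B.4. A non-serious drug side effect is neither device- nor procedure-related. Whether a nerve block or an ablation given as CMM counts as a procedure is not stated. The Reporting part points to Section C for a list, but Section C describes risks of SCS, surgery, system revision, imaging and pregnancy, and no harms of CMM.

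A coordinator who takes the B.7.6 sentence as the instruction for the form could therefore enter implant and stimulation events and leave out non-serious CMM events. One who works from B.8.2 would enter everything. At stake is the secondary safety comparison: the rates in SAP 5.9 can be no more complete than the forms behind them, and completeness would depend on arm and on site.

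**Working it through.** The documents state no adverse event rate, so there is no planned figure to reproduce. The check is a comparison of texts, followed by an illustration on assumed rates.

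**Step 1. Which events reach the form under each rule**

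| Type of event | B.7.6 sentence read as a limit | B.8.2 rule |
|---|---|---|
| Serious, any cause, either arm | Recorded (separate SAE rule in the same section) | Recorded |
| Non-serious, device- or implant-related (subjects with SCS) | Recorded | Recorded |
| Non-serious, from a CMM intervention (either arm) | Depends on the undefined word procedure | Recorded |
| Non-serious, from CMM medication (either arm) | Not called for | Recorded |
| Non-serious, unrelated to any treatment (either arm) | Not called for | Recorded |

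Back or leg pain that is not serious is exempt from mandatory reporting under both rules. The two rules differ only in the last three rows. Those rows apply to both arms, because B.4 gives the test arm CMM as well. Until crossover, the second row applies to the test arm alone. The rows at risk are therefore a larger share of all events in the control arm.

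**Step 2. Illustration for the control arm (assumed rates)**

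Inputs: 150 randomized 1:1 (protocol B.5.5) gives 150 / 2 = 75 control subjects. Assume that a proportion r of them have at least one event (20%, 40% or 60%). Of those, assume that a share s (25% to 90%) have only non-serious events outside the device or procedure category.

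Recorded rate = r × (1 − s).

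| True r | Subjects, 75 × r | Recorded, s = 25% | Recorded, s = 90% |
|---|---|---|---|
| 20% | 15 | 0.20 × 0.75 = 15% | 0.20 × 0.10 = 2% |
| 40% | 30 | 0.40 × 0.75 = 30% (22.5 subjects) | 0.40 × 0.10 = 4% (3 subjects) |
| 60% | 45 | 0.60 × 0.75 = 45% | 0.60 × 0.10 = 6% |

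Under the B.8.2 rule s has no effect, and the recorded rate equals r.

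**Step 3. Direction of the distortion between arms**

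SAP 5.9 reports subjects with at least one event. Suppose that both arms share the same background r and s, and that a proportion d of test subjects independently have a device or implant event, always recorded.

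- True difference, test minus control: [r + d(1 − r)] − r = d(1 − r).
- Recorded difference under the restrictive reading: d[1 − r(1 − s)].
- Ratio of recorded to true difference: [1 − r(1 − s)] / (1 − r).

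With r = 40%, the ratio is 0.70 / 0.60 = 1.17 at s = 25% and 0.96 / 0.60 = 1.60 at s = 90%. The ratio exceeds 1 whenever r and s are above zero, so the excess of events in the SCS arm is overstated and CMM looks safer by comparison.

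**The case against.** The strongest reply is that the protocol, read as a whole, asks for all adverse events. The B.7.6 sentence does not say that other events are left out. Its own section goes on to discuss all AEs, asks for relationship to device or procedure on each reported event (a field with little purpose if only related events are entered), and has all AEs followed to resolution. The definition ignores relatedness, the pain exemption makes sense only if events are otherwise reportable, and control visits include an adverse event assessment. On this view there is one loose sentence among several clear ones. The SAP phrase governs which details are documented, while the tabulation already covers all AEs by relatedness. Safety is descriptive, with no hypothesis or success criterion attached.

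Much of this stands. It defeats a stronger reading that a reader might infer: that the protocol records device events only, so the control arm's harms are bound to be undercounted, perhaps to nearly nothing. The documents do not support that. All SAEs are reportable in both arms, CMM interventions may count as procedures, and several sections call for full capture.

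The reply does not remove the conflict. The qualifier sits in the sentence that tells sites what to put on the form, and no text gives B.8.2 precedence. A promise to tabulate all reported events cannot restore events that were never entered. The documents also mention relationship only to device or procedure. Even with full capture, they name no category for attributing an event to CMM, although the form itself is not among the documents and may have one.

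**Conclusion.** The inconsistency is real. Its consequence is a conditional risk, limited to non-serious events. If some sites apply the B.7.6 sentence as a limit, CMM-related and unrelated non-serious events may be missed in both arms. They form a larger share of the control arm's events, and capture would differ between sites.

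The size cannot be derived from the documents. It is zero if every site follows B.8.2. The illustrated losses rest wholly on assumed rates, and the ratio also assumes independence and an equal CMM event burden in the two arms. A reader might infer that the recorded control rate could fall to zero. That would require that no affected subject has a serious event and that no CMM intervention counts as a procedure, and the documents establish neither.

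A reader might also suspect a bias in favour of the device. The direction is the opposite: missing CMM events make CMM alone look safer. The primary endpoint is not affected.

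**What to change.** 1. **Protocol B.7.6, Reporting.** Reword the capture sentence so that all adverse events in both arms, whether or not related to the device, a procedure or CMM, are entered on the form from enrollment to study completion. Keep the existing exception for back and leg pain. This brings it into line with the definition in B.7.6 and with B.8.2.
2. **Meaning of procedure.** State whether the word includes interventions given as CMM.
3. **Relationship.** Record relationship to CMM alongside device and procedure, if the adverse event form does not already do so.
4. **SAP 5.9.** Replace the study-related wording with all captured adverse events, tabulated by arm and by relationship.

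The cost is one protocol sentence, a clarification, possibly one form field and one SAP line, plus some additional forms at sites that were following the B.7.6 sentence. Because events are already asked about at visits in both arms, the added work is mainly transcription. Treatment, endpoints and sample size do not change. The change is best made while events can still be captured prospectively, since missed non-serious events may be hard to recover at analysis.

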## B.8. Evaluation Criteria

Study personnel will be appropriately trained for administration of each test.

### B.8.1. Effectiveness

Results of the tests and standard questionnaires will be recorded in Case Report Forms at Baseline and during follow-up visits. Changes from Baseline will be calculated and compared between the two groups.

Effectiveness will be measured for each subject using the following tests:

- **Pain Visual Analog** The 10 cm visual analog scale (VAS) is a well validated and widely used scaled psychometric instrument to report pain severity. Subjects will score the severity of pain on a 10 cm line, with 0 indicating no pain and 10 indicating the worst pain imaginable. Subjects will complete a chronic back pain VAS in the clinic during scheduled study visits. Subjects will serve as their own control for the pain relief endpoint. Each subject's baseline pain score will be compared to the score at follow-up visits. Mean changes from baseline will be calculated for the entire cohort. The percentage of subjects who achieved  $\geq 50\%$  (back) pain relief will also be calculated based on VAS changes from baseline. VAS scores collected during the study visits will be used for the primary endpoint.

- [REDACTED]
- [REDACTED]
- [REDACTED]
- [REDACTED]

- [REDACTED]
- [REDACTED]
- [REDACTED]

### **B.8.2. Safety Measurements**

**Adverse Events:** Subjects will be assessed for adverse events starting at enrollment and continuing through to study completion. If an adverse event occurs, an adverse event CRF will be completed. The event will be followed until resolution or determination that the subject's condition is stable.

The Investigators shall categorize all adverse events for seriousness, severity, and relationship. All determinations of severity, device relation, and resolution are made by the Investigator and not by the Sponsor.

For purposes of consistent adverse event reporting and analysis, adverse events will be categorized using the Medical Dictionary for Regulatory Activities (MedDRA®) terminology, consistent with the *MedDRA® Term Selection: Points to Consider* document. Events are grouped by System Organ Classification (SOC) and Preferred Term (PT), according to diagnosis and/or event description as provided by the Investigator on the case report form.

### **B.8.3. Health Economic Measures**

Costs and health outcomes (in terms of life-years and quality-adjusted life-years [QALYs]) associated will be captured from healthcare utilization data [REDACTED]

### **B.8.2. Definition of Success**

The subject's self-reported pain intensity score based on the 10 cm Visual Analog Scale (VAS) is considered the outcome measure for the efficacy component of the primary endpoint. VAS is a widely used outcome measure in assessing pain. It is a reliable and valid method, which is easy to administer, and requires minimal training for the test administrator. VAS scores will be collected for both back and leg pain.

Study success will be declared if the superiority test for the primary effectiveness endpoint is statistically significant.

There are no additional pre-specified subject or study-level success criteria for secondary and tertiary endpoints.

## **B.9. Data Collection and Analysis**

### **B.9.1. Data Collection**

Study data will be collected using a secure Electronic Data Capture (EDC) system. Each data field completed via the EDC system is expected to have a verifiable source document. The clinical site will enter the data from the source document directly into the EDC system. Subject confidentiality will be maintained, and each subject will be identified only by the assigned study subject number. Subject names will not be collected.

Data collection is summarized in Table 1a (DTM™ SCS test arm) & 1b (CMM control arm).

The study data collection from the subjects (which are European citizens) will be processed in accordance with the provisions of Regulation 2016/679 of the European Parliament and the Council of April 27, 2016 on the protection of natural persons in regarding the processing of personal data.

#### **Exceptional procedure - in case of exceptional circumstances** (e.g. Covid-19 pandemic)

Remote data collection from the subjects is allowed. This should be evaluated on a case by case basis, pending Investigator's approval based on safety and clinical condition, follow-up visits may be temporarily completed by alternative means.

- Visit windows remain in place as described by the Clinical Investigation Plan (CIP) and should be maintained as much as possible. Subjects should be contacted via phone to confirm AEs, medications and concurrent procedures. All questionnaires required at a visit should be obtained via phone, email or via mail based on site and/or subject preference.
- If by phone: site staff will read each question to the subject and record their answers. The site staff should initial and date the bottom of each form and indicate that this was completed via phone.
- If by email: the site staff should send the provided pdf questionnaires and certification statement to the subjects to complete and return. Subjects can either print and manually complete or complete the forms electronically.
  - If manually completed (printed): the subject will be instructed to initial and date each page and scan and email or mail the responses back to the sites.
  - If the forms are completed electronically: the subject will be instructed to complete the questionnaires and certification statement and return the responses to the site. Ideally, questionnaires will be completed and returned to the site within 3 business days.
- If the questionnaires are sent in hard copy by mail: the subjects should be instructed to complete the questionnaires and initial and date each page after completion and return to site as soon as possible. Ideally, within 3 business days of receipt.

Source documentation should clearly describe the process utilized for each subject at each visit when these alternative methods are utilized.

Enrolment/Entry criteria visits, procedural visits (trial and IPG) and any unscheduled visits required for adverse events obviously should continue to be performed in office when possible. If feasible, remote programming ( DTM™ SCS arm) and/or remote treatment consultation (CMM arm) can be performed.

The preferred method of data collection for this study is an in-office visit, however; until such a time as deemed safe to return to normal operations, we do not want to place the patients and study partners at undue risk.

**Table 1a - Schedule of Study Activities for the Test arm (DTMTM SCS)**

Assessment	Pre-Trial		Trial Phase		Permanent Implant Phase						
	Baseline	Enrollment /Entry Criteria	End of Trial (EoT)	Trial Implant	0-30 d from Trial Implant	0-90 d from EoT	0-14 d from Perm Implant	2-3 Weeks before 12 Month Visit	2-3 Weeks before 9 Month Visit	2-3 Weeks before 6 Month Visit	2-3 Weeks before 3 Month Visit
Window Visit	Might be combined into one visit, if all enrollment and entry criteria are fulfilled at time of baseline assessment										
Informed Consent*	X		X	X							
Medication Usage	X	X									
Pain Intensity (VAS)	X			X							
Eligibility criteria	X										
Pregnancy Test	[X]			[X]							
Medical/Surgical History	X										
AP/Lateral X-Rays	[REDACTED]		X	X	X		[X]	[X]	X	X	X
Healthcare Utilization			X						X	X	[X]
Adverse Event Monitoring			X	X	X	X	X	X	X	[X]	[X]
Device Programming §				X				X	[X]	[X]	
Cross over									[X]	[X]	
Study Completion				[X]	[X]	[X]	[X]	[X]	[X]	[X]	X

[X] Optional activity.

\*For subjects consented prior to the EC approval of the revised consent, they may be reconsented at any study visit.

§As per the IntellisTM neurostimulator instructions for use. This may also include paresthesia testing.

Unscheduled visit: VAS, Adverse Event monitoring and medication to be collected

